**Table 9-3. Exploratory Efficacy Endpoint Summary Table**

Endpoint	Primary Summary and Analysis Method

## **9.6 Safety Analyses**

In the safety analysis, data up to the end of study will be summarized in the final analysis.

### **9.6.1 Adverse Events**

The Medical Dictionary for Regulatory Activities (MedDRA) version **26.0** or later will be used to code all events categorized as adverse events to a system organ class and a preferred term. The severity of each event will be graded using Common Terminology Criteria for Adverse Events (CTCAE) version 5.

The subject incidence of adverse events will be summarized for all treatment-emergent adverse events, serious adverse events, adverse events leading to discontinuation of investigational product, fatal adverse events, treatment-related adverse events, treatment-related serious adverse events, treatment-related adverse events leading to withdrawal of IP, treatment-related fatal adverse events, and adverse events of interest. Subject incidence of treatment-emergent adverse events identified by COVID-19 standardized MedDRA queries and serious adverse events occurring on or after the COVID-19 infection will also be summarized.

Subject incidence of all treatment-emergent adverse events, serious adverse events, adverse events leading to discontinuation of investigational product, and fatal adverse events will be tabulated by system organ class in alphabetical order and preferred term in descending order of frequency.

Subject incidence of events of interest (standardized MedDRA queries and/or Amgen Medical Queries) will also be summarized according to their categories and preferred term. Events of interest could include but are not limited to hypersensitivity, tachyarrhythmias, tachypnea, hematopoietic cytopenia, eosinophilic disorder, leucocyte changes, infection and infestation, cytokine release syndrome injection site reaction **and drug related hepatic disorder**. Number of episodes and duration of treatment-emergent injection site reactions will be further summarized by treatment group.

Overall summary of subject incidence of treatment-emergent adverse events and by preferred term and worst severity grade will be provided by anti-AMG592 and Anti-IL-2 antibody status.

Summaries of treatment-emergent and serious adverse events will be tabulated by system organ class, preferred term, and grade. An overall summary of adverse events by **severity** grade will be provided.

**Summary of exposure-adjusted subject rates of treatment-emergent adverse events will be tabulated overall and by system organ class and preferred term.**

#### **9.6.2            Laboratory Test Results**

Selected clinical laboratory test results, presented in [Table 9-4](#), change and percent change from baseline will be summarized over time by each treatment group. In addition, shift tables, from baseline to the worst on-study laboratory toxicity based on the CTCAE version 5, will be presented.

Subject incidence of worst post-baseline of eosinophils counts and percentages by the laboratory normal range will be tabulated by treatment group.

**Table 9-4 Selected Safety Laboratory Tests**

Central Laboratory: Chemistry	Central Laboratory: Hematology	Central Laboratory: Urinalysis
Creatinine	RBC	Protein/creatinine ratio
Total bilirubin	Hemoglobin	
ALP	Hematocrit	
AST (SGOT)	Platelets	
ALT (SGPT)	Reticulocytes	
GGT	WBC	
Creatinine clearance by MDRD	Differential	
C-reactive protein	• Eosinophils	
CK	• Lymphocytes	
	• Total neutrophils	

**ALP** = alkaline phosphatase; **ALT** = alanine aminotransferase; **AST** = aspartate aminotransferase; **CK** = creatinine kinase; **GGT** = gamma glutamyl transferase; **MDRD** = Modification of Diet in Renal Disease; **RBC** = red blood cell count; **WBC** = white blood cell count

[figure not shown]

#### **9.6.4            Electrocardiogram**

The electrocardiogram (ECG) measurements from this clinical study were performed as per standard of care for routine safety monitoring, rather than for purposes of assessment of potential QT interval corrected (QTc) effect. Because these evaluations may not necessarily be performed under the rigorous conditions expected to lead to meaningful evaluation of QTc data; neither summaries nor statistical analyses will be

provided, and these data would not be expected to be useful for meta-analysis with data from other trials.

#### **9.6.6 Exposure to Investigational Product**

Descriptive statistics will be produced to describe the exposure to IP by treatment arm. Summary statistics will be provided for the total dose received and total duration of IP exposure by treatment arm.

#### **9.6.7 Exposure to Other Protocol-permitted Therapy**

Other protocol-required therapies for this study are immunomodulators/immunosuppressants, OCS, NSAIDs, topical corticosteroids and topical calcineurin inhibitors and anti-proteinuria agents.

**The baseline exposure to OCS and immunomodulators/immunosuppressants will be summarized using descriptive statistics (number and percentages).**

#### **9.6.8 Exposure to Concomitant Medication**

Not applicable.

### **9.7 Other Analyses**

Medical history will be summarized by SOC and PT and tabulated by treatment group and total using the Safety Analysis Set according to the actual treatment received.

#### **9.7.1 Analyses of Pharmacokinetic Endpoints**

**Amgen Clinical Pharmacology Modeling and Simulation (CPMS) group will conduct PK analysis. Serum concentration data will be summarized by treatment for each PK sampling time point. PK parameters may be summarized if adequately estimated.**

**The descriptive statistics for absolute change from baseline, percentage change from baseline and ratio to baseline will be provided by treatment arms at specified time-points for the endpoints C3, C4, anti-dsDNA antibody and antiphospholipid**

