#### Percent change from baseline

The change from baseline divided by baseline value and multiplied by 100:

(change from baseline / baseline) \* 100.

**If the change from baseline is not equal to zero and the baseline value is zero then percent change from baseline is not defined. If the change from baseline is equal to zero and the baseline value is also zero then percent change from baseline is 100.**

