#### Fold change from baseline or ratio from baseline

Fold change from Baseline equals the post-baseline value divided by the baseline value. If the change from baseline is not equal to 0 and the baseline value is 0 then fold change

is not defined. If the change from baseline is equal to 0 and the baseline value is also 0 then fold change is 1.

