#### **Laboratory Measurements**

**Laboratory measurements that are below the lower quantification limits will be considered equal to the lower limit of quantification for all analyses unless explicitly noted otherwise.**

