## **9. Statistical Methods of Analysis**

### **9.1 General Considerations**

All categorical variables will be summarized using the number and percent of subjects falling into each category and all continuous variable will be summarized using mean, standard error (SE), standard deviation (SD), median, first quartile (Q1), third quartile (Q3), minimum, maximum, and number of subjects with observations. Safety endpoints will be summarized descriptively, including treatment-emergent adverse events and serious adverse events, clinically significant changes in laboratory values and vital signs, and incidence of antidrug antibodies. All safety analyses will be performed using the Safety Analysis Set based on subject's actual treatment received.

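### SAP 9.7.1 summarises antibody ratios to baseline without a geometric mean, so arm means can read high and all-subject medians can be drawn toward 1.00

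*SAP*

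**What the plan says.** SAP 9.7.1, in the paragraph on C3, C4, anti-dsDNA and antiphospholipid antibodies, plans three scales: "The descriptive statistics for absolute change from baseline, percentage change from baseline and ratio to baseline will be provided by treatment arms". SAP 5.5 defines the ratio on the raw scale: "Fold change from Baseline equals the post-baseline value divided by the baseline value".

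SAP 9.1 fixes what is reported: "all continuous variable will be summarized using mean, standard error (SE), standard deviation (SD), median, first quartile (Q1), third quartile (Q3), minimum, maximum". Neither section plans a log-scale summary.

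For the selected safety tests in Table 9-4, SAP 9.6.2 plans the value, and "change and percent change from baseline will be summarized over time by each treatment group". No ratio is planned for them.

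SAP 8.3 adds a substitution rule: "Laboratory measurements that are below the lower quantification limits will be considered equal to the lower limit of quantification for all analyses", unless noted otherwise. The visible text gives no quantification limit, no expected share of values below one, and no plan to count them.

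SAP 10 replaces the between-arm comparisons of the final analysis with descriptive statistics by arm.

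**The concern.** Ratios are multiplicative. A halving and a doubling cancel on the log scale, but the arithmetic mean of 0.5 and 2 is 1.25. The mean raw ratio, and with it the mean percent change, therefore rises with within-subject noise. The planned SE and SD describe the same skewed quantity.

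The median does not have this fault, but the substitution rule affects it in another way. A subject below the limit at both visits has a ratio of exactly 1 and a percent change of exactly 0, whatever happened to the true level. Pooling such subjects with those who have measurable antibody draws the median toward no change.

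With no between-arm model or test left, readers will take these tables at face value. A modest fall in autoantibody could then show as a smaller fall or none. For anti-dsDNA, absolute change is an imperfect substitute: SAP 5.6 uses cut-offs of 15 IU/mL in Asia and 75 IU/mL elsewhere, so pooled absolute changes mix two scales and the relative summaries carry more of the weight.

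**Working it through.** **Inputs.** The documents give the ratio definition (SAP 5.5), the list of statistics (SAP 9.1) and the substitution rule (SAP 8.3). They give no within-subject variability, no limit and no share below it, so these are assumed and shown as ranges. The plan states no figure on this point, so there is none to reproduce.

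**1. Mean ratio.** Let log baseline and log follow-up carry independent normal errors with SD s. The log ratio then has SD t = s√2. With true ratio m, the median and geometric mean ratio equal m, and the mean ratio is m × exp(t²/2) = m × exp(s²).

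| Assumed variability | Mean ratio, m = 1 | Mean ratio, m = 0.75 | Geometric mean ratio |
|---|---|---|---|
| s = 0.3 (t = 0.42) | exp(0.09) = 1.094 (+9%) | 0.821 (−18%) | 1.00 / 0.75 |
| s = 0.5 (t = 0.71) | exp(0.25) = 1.284 (+28%) | 0.963 (−4%) | 1.00 / 0.75 |
| t = 0.1 (stable) | exp(0.005) = 1.005 (+0.5%) | 0.754 (−25%) | 1.00 / 0.75 |
| t = 0.2 (stable) | exp(0.02) = 1.020 (+2%) | 0.765 (−23%) | 1.00 / 0.75 |

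**2. Median.** Let q be the share of subjects at the limit at both visits, and f the probability that one of the others falls, f = Φ(−ln m / t). The all-subject median is exactly 1.00 when (1 − q)f ≤ 0.5, that is q ≥ 1 − 0.5/f.

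- m = 0.7, t = 0.5: f = Φ(0.713) = 0.762, so q ≥ 0.344.
- Lowest threshold in the range tried (m = 0.85, t = 1.0): f = 0.565, q ≥ 0.114.
- Highest (m = 0.5, t = 0.3): f = 0.990, q ≥ 0.495.

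For m = 0.7 and t = 0.5, the all-subject median is 0.70, 0.75, 0.82, 0.93, 1.00 and 1.00 at q = 0, 0.1, 0.2, 0.3, 0.4 and 0.5. Below the threshold it is pulled toward 1 but not held there.

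**3. What the geometric mean ratio (GMR) recovers.** A simulation used 1,000,000 subjects per setting, a between-subject log SD of 1, a per-visit log SD of 0.35 and the limit at a chosen percentile of baseline.

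| Limit at percentile | Median, all (30% fall) | GMR, all (30% fall) | GMR, baseline above limit (30% fall) | GMR, baseline above limit (no change) |
|---|---|---|---|---|
| 10th | 0.76 | 0.73 | 0.71 | 0.99 |
| 30th | 0.91 | 0.80 | 0.72 | 0.97 |
| 50th | 1.00 | 0.86 | 0.72 | 0.96 |
| 70th | 1.00 | 0.92 | 0.74 | 0.94 |

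The all-subject GMR removes the upward bias but is still diluted. Restricting to subjects above the limit removes most of the dilution and introduces regression to the mean (last column).

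**4. Selecting on a high baseline.** With no true change and a between-subject log SD of 1, the GMR in the top fraction p at baseline is exp[−s²/√(1+s²) × φ(z)/p], where z is the standard normal cut-off for the top fraction p. For p = 0.5 and 0.3 this is 0.93 and 0.91 at s = 0.3, and 0.84 and 0.77 at s = 0.5. Subjects chosen for low complement would likewise appear to rise.

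**5. Zeros.** For a zero that stays zero, SAP 5.5 sets fold change to 1, which corresponds to a percent change of 0. The same section says: "If the change from baseline is equal to zero and the baseline value is also zero then percent change from baseline is 100". Any test that can be recorded as zero, such as an eosinophil count, could thus contribute +100 with no change.

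**The case against.** The plan is not confined to arithmetic means. Median and quartiles are reported, and the median ratio is not biased upward. Mean absolute change is reported too, and it does not drift upward under no change. Even with the median at 1.00, the first quartile still shows a 30% fall (0.63 at q = 0.4 and 0.70 at q = 0.5, with t = 0.5). All of this stands.

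Placebo is summarised in the same way. With equal spread every arm carries the same factor, and 0.75 × exp(s²) divided by exp(s²) is 0.75, so the within-arm reading suffers and the contrast does not. That stands for equal spread only. If only some treated subjects respond, spread may widen: with assumed t = 0.5 on placebo and 0.8 on active, and true ratios 1 and 0.75, the means are exp(0.125) = 1.13 and 0.75 × exp(0.32) = 1.03. Their quotient is 0.91, not 0.75.

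The two effects also do not occur together at full size. If only 45% of subjects are above the limit and the rest have ratio 1, the mean excess falls to 0.45 × 9.4% = 4% and 0.45 × 28.4% = 13%.

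For safety, SAP 9.6.2 also plans CTCAE shift tables and eosinophil incidence against the normal range, which this point does not touch. Exploratory endpoints are blank in the public text, and SAP 9.7.3 allows further biomarker analyses, so other summaries may exist.

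**Conclusion.** The point holds in limited form. A raw-scale mean ratio or percent change without a geometric mean is a poor summary for variable analytes: about +9% to +28% with no true change if the per-visit log SD is 0.3 to 0.5, and negligible if the log-ratio SD is 0.1 to 0.2. The documents do not show which analyte falls where; wide variability in antibody levels is an assumption.

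A reader might infer that medians will sit at 1.00 for antibodies, complement and safety tests alike. The documents do not support that. It needs roughly 11% to 50% of subjects at the limit at both visits, depending on effect and spread. This is plausible for antibodies: protocol inclusion criterion 103 admits subjects without anti-dsDNA, SAP 9.4 tabulates an anti-dsDNA-negative group, and antiphospholipid positivity is not an entry requirement. Nothing shows it for C3, C4 or the safety tests. Nor should a reader infer that the comparison with placebo is lost, or that safety-test ratios are affected, since none are planned.

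The point is minor. No primary or visible secondary efficacy endpoint rests on these summaries.

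**What to change.** - In SAP 9.7.1, add the geometric mean ratio (exponentiated mean log ratio) with 95% confidence interval for anti-dsDNA, anticardiolipin IgG and IgM and beta-2 glycoprotein IgG and IgM, and for C3 and C4 for consistency. Give percent change as 100 × (GMR − 1). Keep median and quartiles. Lupus anticoagulant, which SAP 8.3 derives as positive or negative, has no ratio and stays outside this.
- Report the number of subjects below the limit at each visit, by arm.
- In SAP 9.6.2, do the same for percent change of the skewed tests in Table 9-4 (C-reactive protein, CK, eosinophils), with a stated rule for zeros that also reconciles the two zero-to-zero conventions in SAP 5.5.
- As supportive rows, give anti-dsDNA changes in baseline-positive subjects and C3/C4 changes in baseline-low subjects, using the SAP 9.4 categories. State that these rows are to be read only against placebo, because selection on baseline moves every arm toward the mean.

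The cost is SAP wording, standard output code and a few more table rows. No new data are needed.

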**antibody (anticardiolipin antibody IgG and IgM, beta-2 glycoprotein IgG and IgM and lupus anticoagulant).**

#### **9.7.2 Analyses of Clinical Outcome Assessments**

The PRO endpoints include fatigue standardized score using PROMIS Fatigue SF 7, physical and mental component score and individual domains of the SF 36 v2.

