### 5.5 Arithmetic Calculations

#### Change from baseline

The arithmetic difference between a post-baseline value and baseline for a given timepoint:

(post-baseline value – baseline value).

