### **Lupus anticoagulant**

**Lupus anticoagulant results will be derived as follows:**

- When activated partial thromboplastin time (aPTT)  $\leq 29.4$  seconds, then lupus anticoagulant is 'negative'.
- When aPTT  $\geq 29.4$  seconds and hexagonal phospholipid  $< 11$  seconds, then lupus anticoagulant is 'negative'.
- When aPTT  $\geq 29.4$  seconds and hexagonal phospholipid  $\geq 11$  seconds, then lupus anticoagulant is 'positive'.

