**Lupus anticoagulant results will only be derived for baseline, week 24 and week 52 visits.**

#### **Dates**

Missing and incomplete dates will be imputed as outlined in [Appendix E](#).

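### SAP 9.7.1 plans change, percent change and ratio to baseline for lupus anticoagulant, which SAP 8.3 derives only as negative or positive, by rules that conflict at one aPTT value

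*SAP*

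**What the plan says.** SAP 8.3, under the lupus anticoagulant heading, derives the result from aPTT and the hexagonal phospholipid test by three rules:

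- Rule 1: aPTT at or below 29.4 s is negative, with no condition on hexagonal phospholipid.
- Rule 2: aPTT at or above 29.4 s with hexagonal phospholipid below 11 s is negative.
- Rule 3: aPTT at or above 29.4 s with hexagonal phospholipid of 11 s or more is positive.

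There is no third outcome and no numeric score. The same section fixes the visits: "Lupus anticoagulant results will only be derived for baseline, week 24 and week 52 visits".

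SAP 9.7.1 then states: "The descriptive statistics for absolute change from baseline, percentage change from baseline and ratio to baseline will be provided by treatment arms". The endpoints that follow are C3, C4, anti-dsDNA and antiphospholipid antibodies, the last spelled out as "antibody (anticardiolipin antibody IgG and IgM, beta-2 glycoprotein IgG and IgM and lupus anticoagulant". Lupus anticoagulant is therefore named, not swept in by a general term.

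SAP 5.5 defines change from baseline as "The arithmetic difference between a post-baseline value and baseline for a given timepoint". Percent change is that difference divided by baseline, times 100. Fold change, or ratio, is the post-baseline value divided by baseline. SAP 5.5 also has zero-baseline rules. If baseline is zero and the change is not, percent change and fold change are undefined. If both are zero, percent change is set to 100 and fold change to 1.

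SAP 9.1 has a general rule that categorical variables are summarised by number and percent per category.

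**The concern.** The two instructions do not fit together. One section creates a yes/no variable, and another asks for statistics that need a number on a meaningful scale. A programmer following 9.7.1 literally has to invent a code, and the printed percent changes and ratios would then describe the code as much as the subjects.

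What a reader would want from this marker is the proportion positive in each arm at each visit and, if possible, how many subjects changed status. The statistics named in 9.7.1 are poorly suited to both.

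The second defect is in the derivation itself. Both aPTT conditions include 29.4 s, so one recorded value can satisfy two rules with opposite results.

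**Working it through.** The plan gives no figure of its own to reproduce. The check applies its rules as written.

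**Step 1: the summary statistics.** Inputs are the two outcomes in SAP 8.3 and the formulas in SAP 5.5:

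- change = post − baseline
- percent change = 100 × (post − baseline) / baseline
- ratio = post / baseline

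The numeric code is an assumption, because the SAP gives none. Two are shown: negative/positive as 0/1 and as 1/2.

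| Baseline to post | Coding | Change | Percent change | Ratio |
|---|---|---|---|---|
| Negative to negative | 0/1 | 0 | 100 (zero-baseline rule) | 1 |
| Negative to positive | 0/1 | 1 | undefined | undefined |
| Positive to negative | 0/1 | −1 | −100 | 0 |
| Positive to positive | 0/1 | 0 | 0 | 1 |
| Negative to negative | 1/2 | 0 | 0 | 1 |
| Negative to positive | 1/2 | 1 | 100 | 2 |
| Positive to negative | 1/2 | −1 | −50 | 0.5 |
| Positive to positive | 1/2 | 0 | 0 | 1 |

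The same conversion from negative to positive has no percent change under one code and +100% under the other. A subject who stays negative shows a percent change of 100 under 0/1, although nothing happened, and 0 under 1/2.

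Absolute change is the same under these two codes, because both place the levels one unit apart. Its mean equals (number turning positive − number turning negative) / number assessed. That is a net figure: equal numbers of gains and losses give zero.

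**Step 2: the derivation rules.** The three rules were applied to values on either side of each cut-off.

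| aPTT (s) | Hexagonal phospholipid (s) | Rules met | Result |
|---|---|---|---|
| 29.3 | 10.9, 11.0 or 12 | 1 | negative |
| 29.4 | 10.9 | 1 and 2 | negative (the rules agree) |
| 29.4 | 11.0 or 12 | 1 and 3 | negative and positive: conflict |
| 29.5 | 10.9 | 2 | negative |
| 29.5 | 11.0 or 12 | 3 | positive |

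The conflict arises at one aPTT value only, and only when hexagonal phospholipid is 11 s or more. The cut-off is written to one decimal, so 29.4 s is a value that could be recorded.

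**The case against.** The best reply is that SAP 9.1 already covers this. A negative/positive result is categorical, the general rule gives number and percent, and 8.3 fixes the visits. That stands in part: counts of positives by visit are available under an existing rule. It does not remove the contradiction, because 9.7.1 lists lupus anticoagulant by name and makes no exception for it.

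A second reply is that little depends on it. The study stopped for futility after the third interim analysis, SAP 10 drops statistical comparison of the arms at the final analysis, and lupus anticoagulant is not among the primary or secondary endpoints shown. That is correct and sets the weight of the point. The summary was kept in the reduced plan, though, and a descriptive table still has to be computable.

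Two stronger readings are tempting, and the documents support neither:

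- A reader might infer that every new positive is lost from the percent-change and ratio summaries. That holds under 0/1 coding. The SAP does not specify that coding, and under 1/2 coding none is lost.
- A reader might infer that the plan has no way of showing how many subjects are positive or convert. SAP 9.1 supplies the counts of positives. As for conversions, the exploratory objectives and the body of Table 9-3 are not visible in the public copy, so their absence from the plan cannot be claimed.

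**Conclusion.** Both defects stand on the text. Percent change and ratio to baseline have no meaning for a result that is only negative or positive, since their values follow an arbitrary code. Absolute change gives at most a net count. The mismatch itself needs no coding assumption; only the worked values do. Of the endpoints listed in 9.7.1, only lupus anticoagulant is shown to be affected.

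The overlap at 29.4 s is a separate drafting slip at one boundary point. A reader might suspect that it misclassifies a material number of subjects. The documents give no aPTT distribution from which to judge that, and with a single value involved the number is probably small.

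This is a minor correction to a descriptive summary of one marker. It does not bear on the primary endpoint, the interim futility decision or any comparison between arms.

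**What to change.** In SAP 9.7.1, remove lupus anticoagulant from the list summarised by absolute change, percent change and ratio. State instead that the number and percent negative and positive will be given by arm at baseline, week 24 and week 52, in line with SAP 9.1. A baseline-by-visit shift table would also show conversions in each direction; it is optional, since the counts alone resolve the contradiction.

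In SAP 8.3, make one of the two aPTT inequalities strict so that 29.4 s maps to a single result. The documents do not say which side is intended, so the choice should follow the testing laboratory's definition.

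The cost is two wording edits and one small table. No new data are needed.
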